#### **2.8.1.2 Requirements of ClinicalTrials.gov and EudraCT**

For the legal requirements of ClinicalTrials.gov and EudraCT, two required tables on treatment emergent adverse events which are not serious adverse events and on treatment emergent serious adverse events and SAE suspected to be related to study treatment will be provided by system organ class and preferred term on the Safety set.

If for a same participant, several consecutive AEs (irrespective of study treatment causality, seriousness and severity) occurred with the same SOC and PT:

- a single occurrence will be counted if there is  $\leq 1$  day gap between the end date of the preceding AE and the start date of the consecutive AE
- more than one occurrence will be counted if there is  $> 1$  day gap between the end date of the preceding AE and the start date of the consecutive AE

For occurrence, the presence of at least one SAE / SAE suspected to be related to study treatment / non SAE has to be checked in a block e.g., among AE's in a  $\leq 1$  day gap block, if at least one SAE is occurring, then one occurrence is calculated for that SAE.

The number of deaths resulting from SAEs suspected to be related to study treatment and SAEs irrespective of study treatment relationship will be provided by SOC and PT.

These tables will be provided at the final analysis.

## **2.8.2 Deaths**

Death, if any, will be listed.

## **2.8.3 Laboratory data**

Laboratory parameters will be summarized by presenting descriptive statistics for hematology and biochemistry. The absolute values and change from baseline will be summarized by scheduled visit presenting mean, standard deviation, median, minimum, maximum and number of participants with non-missing data. Change from baseline will be summarized for participants with both baseline and post baseline values.

Shift tables of baseline to the worst post baseline value and to the last post baseline value based on normal ranges will be provided for hematology and biochemistry if normal ranges are available. The measurements on the unscheduled visits will be taken into account for the shift tables.

Incidence rates of notable abnormalities newly occurred after baseline (see [Section 5.4](#)) at any visit (including the unscheduled visits) will be presented. The denominator will be the number of participants at risk (i.e., the number of participants having a baseline measurement not meeting the criteria or missing but having at least one post-baseline measurement).

A listing for participants satisfying at least one criterion for notable abnormalities newly after baseline will be listed by participant and visit. A listing for all parameters with High or/and Low values based on normal range or with abnormality detected will be listed by participant and visit and if normal ranges are available abnormal values will be flagged. However, for the listing of participants with newly occurring liver enzyme abnormalities, all parameters will be listed.

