### **2.5.6 Supportive analyses**

The primary analysis will be repeated, using data from all 14 participants, based on the FAS at the timing of the Week 28 interim analysis. Hypothesis testing will not be performed.

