## **Systemic feature score**

For total score, summary statistics for the observed values and the change/percent change from baseline will be provided by scheduled visit.

For each component score, the number and percentage of participants whose score is 1 (present) will be provided by scheduled visit.

The total score will be calculated by summing the scores of each component and is defined as an integer value 0 to 10. The total score will be calculated only when all components are available.

Each component will be assigned a score of 1 (present) or 0 (absent) as follows:

- Fever [defined as a body temperature  $>37.5^{\circ}\text{C}$  at least once a day during at least 5 consecutive days]
- Rash [defined by the presence of typical salmon-pink rash on the trunk and elsewhere during the febrile episodes]
- Serositis
- Lymphadenopathy [defined by lymph node enlargement to  $>1.5$  cm localized anywhere within the body]
- Hepatomegaly and/or splenomegaly that had been confirmed by ultrasound evaluation

At baseline, laboratory features were considered present based on the following:

- ESR  $\geq 20$  mm/hour
- CRP (observed)  $\geq 10$  mg/liter
- White blood cell (WBC) count  $\geq 12 \times 10^9$ /liter
- Hemoglobin  $\leq 11$  g/dl
- Platelet count  $\geq 400 \times 10^9$ /liter.

During treatment epochs and at follow up visits, the laboratory parameters were scored as follows:

- ESR, score of 0 if  $<20$  mm/hour or if decreased by  $\geq 30\%$  compared to baseline, score of 1 if increased or if decreased by  $<30\%$  compared to baseline
- CRP, score of 0 if  $<10$  mg/liter or if decreased by  $\geq 30\%$  compared to baseline, score of 1 if increased or if decreased by  $<30\%$
- WBC count, score of 0 if  $<12 \times 10^9$ /liter or if decreased by  $\geq 20\%$  compared to baseline, score of 1 if increased or if decreased by  $<20\%$
- Hemoglobin level, score of 0 if  $>11$  g/dl or if increased by  $\geq 20\%$  compared to baseline, but score of 1 if decreased or if increased by  $<20\%$ ;
- Platelet count, score of 0 if  $<400 \times 10^9$ /liter or if decreased by  $\geq 20\%$  compared to baseline, score of 1 if increased or if decreased by  $<20\%$ .

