## 5.4 Clinically notable laboratory values and vital signs

The following defined notable laboratory or vital sign abnormalities will be used.

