#### Newly occurring selected notable laboratory abnormalities :

- Albumin: < LLN
- >3x-, 5x-, 8x-, 10x-, and 20x-ULN elevations of AST, ALT, and either ALT or AST\*
- Any elevations of bilirubin > ULN; elevated bilirubin to >1.5xULN, and to >2xULN\*
- Any elevations of ALP >1.5xULN, >2xULN, >3xULN, >5xULN \*
- Elevation of AST and/or ALT (>3xULN, >5x-, >10x) accompanied by elevated bilirubin (>2xULN)\*
- ALT or AST >3x ULN and TBL >2x-, and ALP <2xULN
- ALP >3x-, 5x ULN and TBL >2xULN
- Gamma-Glutamyl transferase (GGT): > ULN, 3 x ULN, 5 x ULN
- Creatinine (serum):  $\geq 1.5 \times \text{ULN}$
- Creatinine clearance (Cockcroft-Gault formula‡):
  - $\geq 25\%$  decrease from baseline†
  - $\geq 25\%$  decrease from baseline† and  $\geq 3$  months in duration§
  - $\geq 25\%$  decrease from baseline† in combination with protein urine dipstick resulting in new protein  $\geq 1+$  and  $\geq 3$  months in duration§
- Potassium:  $\geq 5.5 \text{ mmol/L}$ , or  $\leq 3.0 \text{ mmol/L}$
- Magnesium:  $\geq 1.5 \text{ mmol/L}$ , or  $\leq 0.5 \text{ mmol/L}$
- Sodium:  $\geq 150 \text{ mmol/L}$ , or  $\leq 130 \text{ mmol/L}$
- Calcium:  $\geq 1.2 \times \text{ULN}$  or < LLN

- Hemoglobin:  $\geq 2$  g/dL decrease from baseline, or  $< 10.0$  g/dL
- Criteria based on CTC grades for hemoglobin: Grade 1 ( $< \text{LLN} - 100$  g/L), Grade 2 ( $< 100 - 80$  g/L), Grade 3 ( $< 80 - 65$  g/L), Grade 4 ( $< 65$  g/L)
- Platelet count:  $< \text{LLN}$
- Criteria based on CTC grades for platelet: Grade 1 ( $< \text{LLN} - 75.0 \times 10^9/\text{L}$ ), Grade 2 ( $< 75.0 - 50.0 \times 10^9/\text{L}$ ), Grade 3 ( $< 50.0 - 25.0 \times 10^9/\text{L}$ ), Grade 4 ( $< 25.0 \times 10^9/\text{L}$ )
- White blood cell count:  $\leq 0.8 \times \text{LLN}$  or  $\geq 1.2 \times \text{ULN}$
- Criteria based on CTC grades for white blood cell count: Grade 1 ( $< \text{LLN} - 3.0 \times 10^9/\text{L}$ ), Grade 2 ( $< 3.0 - 2.0 \times 10^9/\text{L}$ ), Grade 3 ( $< 2.0 - 1.0 \times 10^9/\text{L}$ ), Grade 4 ( $< 1.0 \times 10^9/\text{L}$ )
- Absolute Neutrophils:  $\leq 0.9 \times \text{LLN}$  or  $\geq 1.2 \times \text{ULN}$
- Criteria based on CTC grades for absolute neutrophils: Grade 1 ( $< \text{LLN} - 1.5 \times 10^9/\text{L}$ ), Grade 2 ( $< 1.5 - 1.0 \times 10^9/\text{L}$ ), Grade 3 ( $< 1.0 - 0.5 \times 10^9/\text{L}$ ), Grade 4 ( $< 0.5 \times 10^9/\text{L}$ )

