### **Newly occurring selected notable vital signs abnormalities :**

- Systolic blood pressure:  $\geq 25\%$  decrease or  $\geq 25\%$  increase from baseline.
- Diastolic blood pressure:  $\geq 25\%$  decrease or  $\geq 25\%$  increase from baseline.
- Systolic blood pressure and Diastolic blood pressure: increase to  $\geq 140$  and  $90$ , respectively.
- Pulse:  $\geq 110$  bpm with  $\geq 15\%$  change from baseline, or  $< 50$  bpm with  $\geq 15\%$  change from baseline

\* FDA Guidance for Industry Drug-Induced Liver Injury: Premarketing Clinical Evaluation

Note: Only post-baseline values will be flagged as notable abnormalities

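### Because SAP 5.4 writes CTC Grades 1 to 3 as two-sided bands, the SAP 2.8.3 rule counts an improvement from Grade 2 to Grade 1 as a new laboratory abnormality

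*SAP*

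**What the plan says.** SAP 2.8.3 presents "Incidence rates of notable abnormalities newly occurred after baseline", judged at any visit and including unscheduled visits. The denominator is the participants at risk, defined as "the number of participants having a baseline measurement not meeting the criteria or missing but having at least one post-baseline measurement".

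SAP 5.4 supplies the criteria: "The following defined notable laboratory or vital sign abnormalities will be used". Most are one-sided limits or changes from baseline. The SAP also lists CTC grades for four blood counts, for example "Criteria based on CTC grades for hemoglobin: Grade 1" and "Criteria based on CTC grades for absolute neutrophils: Grade 1". For haemoglobin, Grade 1 runs from below LLN down to 100 g/L, Grade 2 from below 100 to 80, Grade 3 from below 80 to 65, and Grade 4 is below 65. Platelets, white cells and neutrophils are set out in the same way. The upper limit of each band is excluded and Grade 4 is open below, so it is Grades 1 to 3 that are bounded on both sides.

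The only other restriction is the closing note of that section: "Only post-baseline values will be flagged as notable abnormalities". Nothing requires the post-baseline grade to be worse than baseline, keeps only the worst grade, or makes the grades cumulative. Appendix 1 of the protocol has no CTC bands; they appear only in the SAP.

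**The concern.** A participant in a worse grade at baseline does not meet the milder grade's band. The rule therefore places that participant at risk for the milder grade and records an event when recovery passes through it. The count goes in the wrong direction.

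This matters here because low haemoglobin belongs to the disease activity that treatment should correct. In the systemic feature score (SAP 2.7.2), a value of 11 g/dL or less scores a point at baseline, and the point is removed when haemoglobin rises above 11 g/dL or by at least 20%. A good response could thus raise the apparent incidence of new low haemoglobin. SAP 2.8 reports these incidences up to Week 28, up to Week 48 and for the entire treatment period, and the interim analyses support the registration dossier.

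**Working it through.** The documents state no figure on this point, so there is none to reproduce. The check applies the rule to test values and then sizes the effect under stated assumptions.

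**Step 1: the rule as written.** For a criterion C, a participant is at risk if baseline does not meet C (or is missing) and there is a post-baseline value. An event is any post-baseline value that meets C. The LLN for haemoglobin is not given; 110, 115, 120, 130 and 135 g/L were tried, and the results below are the same for all five.

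| Haemoglobin path (g/L) | Direction | New events, bands as written | New events, cumulative limits |
|---|---|---|---|
| 90 to 105 | improves | Grade 1 | none |
| 90 to 105 to 140 | normalises | Grade 1 | none |
| 75 to 90 to 105 | improves | Grade 2 and Grade 1 | none |
| 140 to 105 | worsens | Grade 1 | Grade ≥1 |
| 105 to 90 | worsens | Grade 2 | Grade ≥2 |
| 90 to 92 | same grade | none | none |

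The cumulative limits are <LLN, <100, <80 and <65 g/L. They remove the false events and keep the true ones.

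**Step 2: effect on the percentage.** SAP 2.5.6 refers to an analysis "using data from all 14 participants, based on the FAS at the timing of the Week 28 interim analysis", so N = 14. Suppose, for illustration, that k participants go from 90 to 105 g/L and all others stay normal.

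- k = 1: bands give 1/14 = 7.1%; cumulative limits give 0/13 = 0%.
- k = 3: bands give 3/14 = 21.4%; cumulative limits give 0/11 = 0%.

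If some participants start in Grade 1 they leave the denominator, and each false case weighs more than 7.1 points.

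**Step 3: how many false Grade 1 cases.** Only participants who start below 10 g/dL (100 g/L) can produce one. With baseline haemoglobin assumed normal with mean m and SD 1.4 g/dL, the ceiling is 14 × Φ((10 − m)/1.4). Whether a participant enters the Grade 1 band then depends on the rise. A simulation was run with LLN 12 g/dL, mean rise 0.5 to 2.0 g/dL, within-person SD 0.4 and 12 post-baseline visits, with the rise either immediate or spread over six visits.

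| Baseline mean (g/dL) | Φ((10 − m)/1.4) | Ceiling of 14 | Simulated false cases of 14 |
|---|---|---|---|
| 13 | Φ(−2.14) = 0.016 | 0.2 | about 0.2 |
| 12 | Φ(−1.43) = 0.077 | 1.1 | 0.9 to 1.1 |
| 11 | Φ(−0.71) = 0.238 | 3.3 | 2.3 to 3.2 |
| 10.5 | Φ(−0.36) = 0.360 | 5.0 | 3.2 to 4.9 |

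Every input in Step 3 is an assumption. The baseline mean drives the result; the speed of the rise changes the number of false cases little.

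**Step 4: the other three counts.** Neutrophil Grade 2 begins below 1.5 × 10⁹/L, the same value as the screening exclusion of counts under 1500/mm³ (protocol 5.2). A participant could start in Grade 2 or worse only by falling after screening. For white cells and platelets, the disease features in the documents are high counts (leukocytosis in the Yamaguchi criteria; white cells ≥12 and platelets ≥400 × 10⁹/L in the systemic feature score), so a low baseline grade is not what the plan leads one to expect.

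**The case against.** **Other outputs show the direction.** SAP 5.4 also has one-sided haemoglobin criteria (a fall of at least 2 g/dL, or a value below 10.0 g/dL), and a rise from 90 to 105 g/L is a new event under neither. SAP 2.8.3 adds change from baseline by visit, shift tables and listings by participant. With 14 participants each case can be traced. This stands as a reason why a careful reader is unlikely to be misled for long. It does not correct the CTC rows: the shift tables use normal ranges and not grades, so the improver appears there as low to low, and the notable-abnormality listing selects on the same condition of being new after baseline.

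**The criteria could mean any grade of that parameter.** That reading keeps a baseline Grade 2 participant out of the Grade 1 risk set. The SAP does not say so, and the reading would also remove baseline Grade 1 participants from the risk set for Grades 2 to 4 and hide true worsening.

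**A programmer might take only the worst post-baseline grade.** The text says any visit. Even the worst-grade convention would not be enough: with 90 at baseline and 105 and 108 afterwards, the worst post-baseline grade is Grade 1 and is still counted as new.

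**Stronger readings a reader might infer.** One is that recovery would be reported as treatment-emergent anaemia. SAP 2.8.1 defines treatment-emergent for adverse events, as starting after the first dose or increasing in severity, and an improving laboratory value does not become such an event through this table. Another is that most reported Grade 1 cases will be improvements. That depends on the baseline mean and on the course of the rise, neither of which the documents give. In the systemic feature score list introduced by "At baseline, laboratory features were considered present based on the following", haemoglobin of 11 g/dL or less scores a point, but nothing says how common values below 10 g/dL are.

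**Conclusion.** The point holds as a defect in a stated rule. SAP 2.8.3 and 5.4 together count an improvement from Grade 2 to Grade 1, or from Grade 3 to Grade 2, as a new abnormality, and no other provision undoes it. This conclusion needs no assumption about the data.

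Its reach is limited. It affects the CTC-grade rows of the descriptive incidence table and the matching listing, and mainly haemoglobin. The number of false Grade 1 cases is about 0.2 to 5 of 14 for baseline means of 13 down to 10.5 g/dL, with SD 1.4, LLN 12 and rises of 0.5 to 2.0 g/dL all assumed. At the low end the effect is negligible; at the high end it would dominate the row. It should be corrected because the error runs in the direction of treatment response and is cheap to remove.

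**What to change.** In SAP 5.4, write the CTC criteria as cumulative one-sided limits: haemoglobin <LLN, <100, <80 and <65 g/L, and likewise for platelets, white cells and neutrophils using the limits already listed. Label the rows Grade ≥1, ≥2, ≥3 and 4. Alternatively, keep the bands and add that a grade counts as newly occurring only if it is worse than the baseline grade.

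In SAP 2.8.3, state that for Grade ≥k the at-risk denominator is participants whose baseline grade is below k or whose baseline is missing, and who have at least one post-baseline measurement. This keeps both existing conditions and changes nothing for the criteria that are already one-sided. Apply the same condition to the listing.

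The cost is one sentence and a small programming change. No new data are needed.

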## **2.8.4 Other safety data**

### **2.8.4.1 ECG and cardiac imaging data**

ECG measurements will be summarized by presenting descriptive statistics for the absolute values and changes from baseline by scheduled visit. Change from baseline will be summarized for participants with both baseline and post baseline values.

All information collected will be listed by participant and visit.

#### **2.8.4.2 Vital signs**

Vital signs will be summarized by presenting descriptive statistics for the absolute values and changes from baseline by scheduled visit. Change from baseline will be summarized for participants with both baseline and post baseline values.

Incidence rates of notable abnormalities newly occurred after baseline (see [Section 5.4](#)) at any visit (including the unscheduled visits) will be presented. A listing for participants satisfying at least one criterion for notable abnormalities newly after baseline will be listed by participant and visit.

#### **2.8.4.3 Immunogenicity**

All immunogenicity results will be listed by participant and visit.

#### **2.8.4.4 Adjudication committee data**

MAS adjudication committee is planned. The data reported by the adjudication committee will be listed if any.

### **2.9 Pharmacokinetic endpoints**

Pharmacokinetic parameters will be listed by participant and visit. Descriptive summary statistics will include mean (arithmetic and geometric), SD, CV (arithmetic and geometric), median, minimum, and maximum for the FAS.

### **2.10 PD and PK/PD analyses**

PD parameter (Total IL-1 $\beta$ ) will be summarized by means of arithmetic and geometric mean, SD, CV for arithmetic and geometric mean, median, minimum and maximum for the FAS.

### **2.11 CCI**

A large, stylized red logo consisting of the letters 'CCI' in a bold, sans-serif font. The logo is positioned on the left side of a large black rectangular area that occupies the bottom third of the page.

2.12 CCI

2.13 CCI

CCI

## 2.14 Interim analysis

Two interim analyses will be performed after all participants have completed Week 28 to support the registration dossier, and Week 48 to supplement the dossier with long-term safety and efficacy data. At the interim analysis at Week 28, the primary efficacy analysis will be conducted based on the data up to the time when the first 11 participants have reached Week 28 (or prematurely discontinued prior to Week 28), that is 6Dec2022, CCI [REDACTED].

For the primary efficacy analysis with the first 11 participants, only the endpoints presented below will be analyzed.

- Participant demographics
- Baseline participant characteristics
- Adapted ACR 30/50/70/90/100 response at Week 8 (primary estimand)
- Subgroup analyses based on prior use of Tocilizumab
- Adapted ACR 30/50/70/90/100 response by visit

- Line plot of adapted ACR 30/50/70/90/100
- Successful oral corticosteroid tapering at Week 28
- Successful oral corticosteroid tapering by visit after Week 8
- Prednisone equivalent dose tapered to below 5 mg/day
- Oral corticosteroid dose (mg/day) by visit
- Each component of adapted ACR criteria by visit
- Rash by visit
- DAS28-CRP by visit
- DAS28-CRP response by visit
- EULAR response by visit
- Systemic feature score: Total score by visit
- Systemic feature score: Each component score by visit
- Ferritin level by visit
- Spaghetti plot of ferritin level by visit
- Number of tender/swollen joints
- Standardized CRP within normal range

The analysis set to be used in the analysis presented above will include up to about 11 participants.

After all participants have completed Week 28 and Week 48, two interim analyses will be performed on the efficacy and safety data during the study:

One will be at Week 28, to support the registration dossier and the other will be at Week 48 to supplement the dossier with long-term safety and efficacy data.

At the interim analyses, the data cut-off date for Week 28/Week 48 analysis will be the date of Week 28/Week 48 visit for the last participant. For efficacy analyses including PK/PD and biomarker-related analyses, the data up to Week 28/Week 48 visit for each individual participant will be included. For safety analyses and summaries for treatments, all available data will be included.

At the interim analyses, for participants who discontinued before Week 28/Week 48 visit, the data up to the time of discontinuation will be included for efficacy and safety analyses. For participants who discontinued after Week 28/Week 48 visit, all available data up to the time of discontinuation will be included for safety analyses, but the data up to Week 28/Week 48 will be included for efficacy analyses. For participants who early discontinued, the EOS visit will be remapped using the pre-defined time window before the data cut-off. When the data up to the specific timepoints cannot be extracted, all data available at data base lock will be reported.

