9.3 Study completion and post-study treatment

Study completion is defined as when the last participant finishes their Study Completion visit and any repeat assessments associated with this visit have been documented and followed-up appropriately by the Investigator or, in the event of an early study termination decision, the date of that decision.

All treated participants should have a safety follow-up call conducted 30 days after last administration of study treatment. The information collected is kept as source documentation. All SAEs reported during this time period must be reported as described in [Section 10.1.3](#). Documentation of attempts to contact the participant should be recorded in the source documentation.

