10.1.3 SAE reporting

To ensure participant safety, every SAE, regardless of causality, occurring after the participant has provided informed consent and until 8 weeks after the last administration of study treatment must be reported to Novartis safety within 24 hours of learning of its occurrence. Detailed instructions regarding the submission process and requirements are to be found in the investigator folder provided to each site.

All follow-up information for the SAE including information on complications, progression of the initial SAE and recurrent episodes must be reported as follow-up to the original episode within 24 hours of the investigator receiving the follow-up information. An SAE occurring at a different time interval or otherwise considered completely unrelated to a previously reported one must be reported separately as a new event.

If the SAE is not previously documented in the Investigator’s Brochure or Package Insert (new occurrence) and is thought to be related to the study treatment, a CMO & PS Department associate may urgently require further information from the investigator for health authority reporting. Novartis may need to issue an Investigator Notification (IN) to inform all investigators involved in any study with the same study treatment that this SAE has been reported.

Suspected Unexpected Serious Adverse Reactions (SUSARs) will be collected and reported to the competent authorities and relevant ethics committees in accordance with EU Guidance 2011/C 172/01 or as per national regulatory requirements in participating countries.

Any SAEs experienced after 8 weeks after the last administration of study treatment should only be reported to Novartis Safety if the investigator suspects a causal relationship to study treatment.

SAE Reporting via an Electronic Data Collection Tool

The primary mechanism for reporting an SAE to Novartis will be the electronic data collection tool.

If the electronic system is unavailable, then the site will use the paper SAE data collection tool (see next section) to report the event within 24 hours.

The site will enter the SAE data into the electronic system as soon as it becomes available.

After the study is completed at a given site, the electronic data collection tool will be taken offline to prevent the entry of new data or changes to existing data.

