## **2 Statistical methods**

### **2.1 Data analysis general information**

The statistical analysis will be performed by Novartis using SAS 9.4 TS Level 1M6 or above.

Summary statistics for continuous variables will generally include n, mean, standard deviation, median, minimum, and maximum. For categorical variables, this will generally include frequency and percentage. For selected parameters, 25th and 75th percentiles will also be presented when applicable.

The data cut-off date for Week 28/Week 48 IA will be the date of Week 28/Week 48 visit for the last participant. For efficacy analyses, the data up to Week 28/Week 48 visit for each individual participant will be included. For safety analyses and summaries for treatments, all available data will be included.

No center-specific or stratified analyses will be performed.

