## On-treatment period

Treatment period is from the date of first administration of study treatment to the end of study (EOS) for each participant.

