## **2.8 Safety analyses**

For all safety analyses, the Safety set will be used. The summary tables by visit will include the assessments at the scheduled visits unless otherwise specified. All listings will include unscheduled visits.

At the interim analyses, as described in [Section 2.1](#), all available data at the cut-off date will be included for safety analyses.

For the Week 28 IA, AEs will be summarized up to Week 28 and entire treatment period. Exposure adjusted event rate will be provided for entire treatment period. For laboratory, ECG and vital signs, by-visit summaries will be provided up to Week 28. Incidence rates of notable abnormalities will be provided for the period up to Week 28 and entire treatment period.

For the Week 48 IA, AEs will be summarized up to Week 48 and entire treatment period. Exposure adjusted event rate will be provided for entire treatment period. For laboratory, ECG and vital signs, by-visit summaries will be provided up to Week 48. Incidence rates of notable abnormalities will be provided for the period up to Week 48 and entire treatment period.

For the final analysis, all safety data will be summarized for entire treatment period.

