### **2.8.1 Adverse events (AEs)**

AEs will be coded using the MedDRA dictionary that provides the primary system organ class (SOC) and preferred term (PT) information.

All information obtained on AEs will be displayed by participant. A listing will include all AEs collected on eCRF during the study from screening period and treatment period.

Treatment emergent AEs (events started after the first dose of study medication or events present prior to start of study treatment but increased in severity based on preferred term) will be summarized by presenting, the number and percentage of participants having any AE, having any AE in each primary SOC, and having each individual AE based on the PT. A participant with multiple AEs within a primary SOC is only counted once towards the total of the primary SOC.

The following summary tables will be provided.

- All treatment emergent AEs regardless of study drug relationship by SOC and PT
- All treatment emergent AEs regardless of study drug relationship by maximum severity, SOC and PT
- All treatment emergent AEs regardless of study drug relationship, leading to study drug discontinuation, by SOC and PT
- All treatment emergent AEs regardless of study drug relationship, requiring concomitant medication or non-drug therapy, by SOC and PT
- Treatment emergent serious AEs regardless of study drug relationship by SOC and PT
- Treatment emergent AEs related to study drug treatment by SOC and PT
- Treatment emergent serious AEs related to study drug treatment by SOC and PT
- A summary of death, serious AEs, AEs related to study drug treatment, AEs leading to study drug discontinuation

Exposure adjusted event rate (per 100 participant-years) of treatment emergent AEs will be summarized by SOC and PT. The event rate (ER) per 100 participant-years will be calculated as follows:

$$ER = 100 * \text{total number of occurrence of events} / \text{total participant-years},$$

where total participant-years is the sum of all participants' exposure times, i.e. duration of exposure from the day of the first dose of study treatment to the day of the last study visit.

To support the registration dossier, treatment emergent AEs will also be summarized by SOC, PT and onset period at the 28 Week IA and the 48 week IA using the data up to Week 28 and Week 48, respectively. Deaths, SAEs other than deaths, and AEs causing study treatment discontinuation will also be summarized. The following intervals will be used:

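### The SAP gives conflicting end points for safety data, so SAEs that the protocol requires up to 8 weeks after the last dose may be left out of the safety tables

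*SAP*

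**What the plan says.** **Collection.** Protocol 10.1.3 requires reporting of every SAE, whatever its cause, "occurring after the participant has provided informed consent and until 8 weeks after the last administration of study treatment". Protocol 9.1.1 asks that AEs, SAEs and new or concomitant treatments still be collected, as a minimum, after study treatment is discontinued. Protocol 9.3 adds a "safety follow-up call conducted 30 days after last administration of study treatment".

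**SAP rules that restrict.**
- SAP 2.14, interim analyses, for those who discontinue before Week 28 or Week 48: "the data up to the time of discontinuation will be included for efficacy and safety analyses". The next sentence, on those who discontinue later, again stops their safety data at discontinuation.
- SAP 2.1.1: "Treatment period is from the date of first administration of study treatment to the end of study (EOS) for each participant".
- SAP 2.8: "For the final analysis, all safety data will be summarized for entire treatment period".
- SAP 2.8.1: "A listing will include all AEs collected on eCRF during the study from screening period and treatment period".

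**SAP rules that include.**
- SAP 2.1, in the paragraph on interim cut-offs: "For safety analyses and summaries for treatments, all available data will be included". SAP 2.14 repeats this, and SAP 2.8 says the same for data at the cut-off date.
- The treatment-emergent AE definition in SAP 2.8.1, which matches Protocol 12.5.3, has a start but no end.
- The listings of SAEs (SAP 2.8.1) and of deaths (SAP 2.8.2) state no period limit.

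The exposure-adjusted event rate in SAP 2.8.1 uses person-time from first dose to the last study visit.

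**The concern.** The SAP has no single end date for safety data, and its most specific rule for discontinuers is narrower than what the protocol collects. A programmer who follows the discontinuation rule and one who follows the all-available-data rule would produce different SAE and AESI tables from the same database. These tables are prepared for the registration dossier. Protocol 9.1.1 makes certain serious events grounds for stopping treatment, so the participants whose data might be cut short are not obviously a random subset. If the sponsor does intend to cut the data, that is narrower than Protocol 12.5.3, yet SAP section 4 records no change to the protocol-specified analyses.

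**Working it through.** The documents give no figure on this point to reproduce. The check sets the windows side by side and then bounds the gap in days.

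**1. Collection window after the last dose.** 8 weeks × 7 = 56 days (Protocol 10.1.3). The safety call is at day 30 (Protocol 9.3), so 56 − 30 = 26 days of the SAE window follow the last contact that the protocol times from the last dose.

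**2. Treatment of an SAE that falls after a participant's discontinuation or EOS but within 56 days of the last dose.**

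| Rule | Applies to | Late SAE in the tables? |
|---|---|---|
| Cut at discontinuation (SAP 2.14) | Interim, discontinuers | No, if after discontinuation |
| Treatment period ends at EOS (SAP 2.1.1 with 2.8) | Final analysis | No, if after EOS |
| All available data (SAP 2.1, 2.8, 2.14) | Interim | Yes, up to the cut-off |
| Treatment-emergent definition without an end (SAP 2.8.1) | All analyses | Yes |

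At each analysis at least one rule includes the event and at least one excludes it.

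**3. What discontinuation means.** The protocol glossary separates discontinuation from treatment and from study. If SAP 2.14 means from study, data up to study exit are kept and only later SAE reports are at risk. If it means from treatment, the AE and SAE follow-up required by Protocol 9.1.1 is at risk as well.

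**4. Days of the SAE window outside the cut.** Let d be the days from last dose to the cut. Days outside = max(0, 56 − d). The documents do not fix d, so these values are assumptions:
- d = 0: 56 − 0 = 56 days
- d = 28 (one dosing interval): 56 − 28 = 28 days
- d = 56 or more: 0 days

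These are calendar days, not shares of SAEs.

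**5. Weight of one participant.** N = 14 (SAP 2.5.6). 1/14 = 0.0714, or 7.1 percentage points on an SAE proportion.

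**6. Event rate under the inclusive rules.** An SAE after the last study visit enters the numerator, but its date lies outside the person-time. If person-time for SAE rates alone were extended to day 56 at the final analysis, the addition would range from 0 (d of 56 or more for everyone) to 14 × 56 = 784 days (784/365.25 = 2.15 participant-years). The d = 28 case gives 14 × 28 = 392 days (392/365.25 = 1.07 participant-years).

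**The case against.** The strongest reply is that omission is not settled. The SAP says three times that all available data enter the safety analyses, the treatment-emergent definition would count a late SAE, and the last sentence of SAP 2.14 falls back to everything at database lock when a cut cannot be made. SAEs also have their own listing with no stated period, and MAS adjudication data are to be listed. All of this stands. A reader might infer that late SAEs will certainly be dropped, or that deaths are the only events listed without a period limit; the documents support neither. A reader might also infer a definite downward bias in serious-event rates. That depends on the restrictive reading, and for the exposure-adjusted rate a cut at EOS would roughly match events to person-time.

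The timing of EOS is also open. Protocol section 8 asks for a prompt end-of-treatment or final evaluation visit, while Protocol 9.1.1 requires an EOS visit without dating it. It cannot be assumed that EOS normally falls early in the 56 days.

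The reply does not remove the conflict. The discontinuation rule is the specific one for these participants, comes after the general one in the same section, and is stated twice. Its second sentence separates safety from efficacy and still cuts safety. The database-lock fallback applies only when extraction fails.

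**Conclusion.** The point holds as an internal contradiction with a possible loss of required data, and the text should be changed. Two separate limits are involved: the discontinuation cut applies at the interim analyses only, while the EOS limit on the final analysis comes from the period definition. Under either, SAEs that the protocol requires may be missing from the SAE and AESI tables. Under the inclusive rules they appear, but the event rate counts events outside its denominator.

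The number of SAEs affected cannot be known from the documents. Depending on when discontinuation or EOS falls, between 0 and 56 days of the 56-day window lie outside the tables, and each omitted participant out of 14 would move an SAE proportion by 7.1 points. The primary efficacy analysis is not affected.

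**What to change.** 1. **SAP 2.14.** Limit the discontinuation cut to efficacy in both sentences, so that discontinuers' safety data follow the all-available-data rule up to the cut-off.
2. **SAP 2.1.1 and 2.8.** State that SAE and serious AESI tables and listings include all SAEs to the later of EOS and 8 weeks after the last dose, capped at the cut-off for an interim analysis.
3. **Non-serious events.** Keep non-serious treatment-emergent AE summaries and their rates to the period in which those events are systematically collected. The 8-week requirement covers SAEs only; running every AE table and its person-time to day 56 would add days on which non-serious AEs may not be captured, and so dilute their rates.
4. **Event rates.** Count only events inside the person-time window, or extend the person-time for SAE rates alone.

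The cost is SAP wording and a date flag in the programs, with no new data. SAE counts may rise slightly and may include events under later therapy; these can be flagged as post-treatment.
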